VARIABLES	
Primary Endpoints:
 
1- Primary Safety:
 
 - Incidence of serious/non-serious adverse events 
2- Primary Efficacy:
 
 - Complete resolution for pelvi-abdominal infection based on pelvi-abdominal ultrasound and others and/or clinical response - Complete healing of the of post-operative wounds 
Secondary Endpoints:
 
1- Secondary Safety:
 
 - Presence of any signs/symptoms of post-operative wound infection such as redness, fever or wound discharge. - Change in Total Leukocyte count and Liver enzymes (SGOT, SGPT) between baseline (visit 1) to End of study visit (Follow up 2 V) 
2- Secondary Efficacy:
 
 - Describe complete resolution, improvement, failure or relapse of pelvi-abdominal infection based on pelvi-abdominal ultrasound and others and/or clinical response - Days for complete healing of post-operative wounds after 8 days of treatment (Follow-up 1 V) & 15 days of treatment (End of study visit) between the 2 groups
ASSESSMENT SCHEDULE	
Subjects will be enrolled for 12 months including screening visit
 
 ➤ Visit 1: Screening and treatment initiation visit, Day 0 ➤ Follow-up 1 visit: Day 8 (+/-) 3 days ➤ Follow-up 2 visit & End of study visit: Day 15 (+/-) 3 days
DATA SOURCES	All visits' assessments will be kept in the source files for each patient and in Case Report Form (CRF), which will be verified by the responsible Clinical Research Associate (CRA).
STUDY SIZE	312 patients with pelvi-abdominal infection and/or who started IV antibiotics in post-operative period, for pelvi-

	
abdominal surgeries. They will be randomized by computer, into 2 treatment groups; Ciprofloxacin[®] tablets (Ciprofloxacin/Metronidazole) versus currently used Ciprofloxacin Tablets & Metronidazole tablets, from the surgical department in Menoufia University Hospital and some patients might be referred from other departments in Menoufia University Hospital such as and not limited to; the department of Gynecology and Obstetrics

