10.7.6 Primary Safety analysis

A. Number of participants experiencing Serious Adverse Events (SAEs). [Time Frame: visit 1 to End of study visit].

- Frequency distribution (number & percent) of occurrence of SAEs necessitating a change or discontinuation of treatment. Chi² test will be used to determine *p*-value and significance between the 2 groups.
- Frequency distribution (number & percent) of type and severity of SAEs. Chi² test will be used to determine *p*-value and significance between the 2 groups.

B. Number of participants experiencing Adverse Events (AEs) leading to permanent discontinuation of the study drug. [Time Frame: visit 1 to End of study visit].

- Frequency distribution (number & percent) of causes of treatment discontinuations. Chi² test will be used to determine *p*-value and significance between the 2 groups.
- Frequency distribution (number & percent) of occurrence of AEs necessitating a change or discontinuation of treatment. Chi² test will be used to determine *p*-value and significance between the 2 groups.

- Frequency distribution (number & percent) of type and severity of AEs. Chi² test will be used to determine *p*-value and significance between the 2 groups.

10.7.7 Primary Efficacy analysis:

A. Complete resolution for Pelvi- abdominal infection based on pelvi-abdominal Ultrasound

- Frequency distribution (number & percent) of complete resolution for pelvi-abdominal infection. Chi² test will be used to determine *p*-value and significance between the 2 groups.

B. Complete healing of the post-operative wounds [Time Frame: Follow-up 1 V to End of study visit].

- Frequency distribution (number & percent) of complete healing of the post-operative wounds. Chi² test will be used to determine *p*-value and significance between the 2 groups.
- Frequency distribution (number & percent) of incomplete healing of the post-operative wounds. Chi² test will be used to determine *p*-value and significance between the 2 groups.
- Frequency distribution (number & percent) of no healing of the post-operative wounds. Chi² test will be used to determine *p*-value and significance between the 2 groups.

10.7.8 Secondary Safety analysis:

A. Presence of any signs/symptoms of post-operative wound infection such as redness, fever or wound discharge [Time Frame: visit 1 to End of study visit].

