Frequency distribution (number & percent) of presence of any signs/symptoms of post-operative wound infection such as redness, fever or wound discharge. Chi² test will be used to determine *p*-value and significance between the 2 groups.

B. Change in Total leukocytes count between baseline (visit 1) to End of study visit

Descriptive analysis (mean, Standard Deviation, Median, Interquartile Range, Minimum and Maximum) of total leucocyte will be from baseline (visit 1) to End of study visit. Percent change will be calculated between baseline to End of study. Paired t-test will be used to determine *p*-value and significance between baseline and at the end of the study. Unpaired t-test will be used to determine the *p*-value and significance between Changes in total leucocyte between 2 groups.

C. Change in Liver enzymes (SGOT) between baseline (visit 1) to End of study visit

Descriptive analysis (mean, Standard Deviation, Median, Interquartile Range, Minimum and Maximum) of Liver enzymes (SGOT) will be from baseline (visit 1) to End of study visit. Percent change will be calculated between baseline to End of study. Paired t-test will be used to determine *p*-value and significance between baseline and at the end of the study. Unpaired t-test will be used to determine the *p*-value and significance between Changes in Liver enzymes (SGOT) between 2 groups.

D. Change in Liver enzymes (SGPT) between baseline (visit 1) to End of study visit

Descriptive analysis (mean, Standard Deviation, Median, Interquartile Range, Minimum and Maximum) of Liver enzymes (SGPT) will be from baseline (visit 1) to End of study visit. Percent change will be calculated between baseline to End of study. Paired t-test will be used to determine *p*-value and significance between baseline and at the end of the study. Unpaired t-test will be used to determine the *p*-value and significance between Changes in Liver enzymes (SGPT) between 2 groups.

10.7.9 Secondary Efficacy analysis:

A. Complete resolution, improvement, failure or relapse of Pelvi- abdominal infection

- Frequency distribution (number & percent) of complete resolution, improvement, failure or relapse for Pelvi- abdominal infection. Chi² test will be used to determine *p*-value and significance between the 2 groups.
- Frequency distribution (number & percent) of improvement for Pelvi- abdominal infection. Chi² test will be used to determine *p*-value and significance between the 2 groups.

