- Presence of any signs/symptoms of post-operative wound infection such as redness, fever or wound discharge will be recorded (in case of post-operative subjects)
- Child-Pugh Score will be calculated for liver impairment and pelvi-abdominal Ultrasound and others will be done
- Lab results will be checked for: (Fasting Blood Sugar (FBS), Total leukocytes count, liver enzymes (SGOT & SGPT), Total Bilirubin and S. Creatinine), and Serum β -HCG for females of child bearing potential only
- The Investigator will keep a log of all subjects, who will sign the ICF. Even if the subject would not pass the screening, his/her signed consent form will be retained

in the Investigator file and will be considered as screening failure. The reason(s) for screen failure will be recorded in the screen failure form in the screening log.

- All data related to screening visit must be reviewed (signed and dated) by the Investigator to ensure that the subject will be eligible for the study, before dispensing the study drug.
- Randomization will be done and subjects will be administered the study products; either Ciprofloxacin® tablets or Ciprofloxacin Tablets & Metronidazole tablets.
- Study products sufficient for the next 7 days will be supplied; either Ciprofloxacin® tablets or Ciprofloxacin Tablets & Metronidazole tablets, and storage conditions will be explained. Study products supplied will be recorded.
- Subjects will be asked to come after 7 days of treatment and bring the empty blisters of medication received, with window of 3 days.

In case of any premature discontinuation of the study, the subject will be, if possible, called in for a last visit. Even if the subject was not able to attend the last visit, the End of Study Form must be completed.

Child-Pugh Score will be recorded, as follows:

The score employs five clinical measures of liver disease. Each measure is scored 1-3, with 3 indicating most severe derangement.^[20]

Table 2: Child-Pugh Score

Measure	1 point	2 points	3 points
Total bilirubin, µmol/l (mg/dl)	<34 (<2)	34-50 (2-3)	>50 (>3)
Serum albumin, g/dl	>3.5	2.8-3.5	<2.8
Prothrombin time, prolongation (secs)	<4.0	4.0-6.0	> 6.0
Ascites	None	Mild	Moderate to Severe
Hepatic encephalopathy	None	Grade I-II (or suppressed with medication)	Grade III-IV (or refractory)

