The physician is responsible for the safety of the patient. The sponsor is responsible for the safety of his product and for reporting safety issues to the regulatory bodies according to appropriate regulations. In order for all parties to comply with their responsibilities, it is important that the physician documents and processes quality and safety issues in the following manner.

13.1 Adverse Events (AEs):

An AE is any undesirable medical event occurring to a subject in a clinical trial, whether or not considered related to the trial product(s). This includes events not seen at baseline or worsened if present at baseline. The following will not be recorded as AEs, if recorded at screening visit: Pre-existing conditions found as a result of screening procedures.

Assessment of Intensity/Severity:

The intensity or severity of an AE is defined as follows :

- Mild: Transient symptoms, no interference with the subject's daily activities.
- Moderate: Marked symptoms, moderate interference with the subject's daily activities.
- Severe: Considerable interference with the subject's daily activities, unacceptable

Assessment of Causality (as per WHO-UMC)

The **relationship** of each AE to the study drug where there is a demonstrable cause-effect association between two events, assessed by the investigator:

Causality Term	Assessment of Causality
Certain	
 •Event or laboratory test abnormality, with plausible time relationship to drug intake •Cannot be explained by disease or other drugs •Response to withdrawal plausible (pharmacologically, pathologically) •Event definitive pharmacologically or phenomenological (i.e. an objective and specific medical disorder or a recognized pharmacological phenomenon) • Re-challenge satisfactory, if necessary
Probable /Likely	
 •Event or laboratory test abnormality, with reasonable time relationship to drug intake •Unlikely to be attributed to disease or other drugs •Response to withdrawal clinically reasonable • Re-challenge not required
Possible	
 •Event or laboratory test abnormality, with reasonable time relationship to drug intake •Could also be explained by disease or other drugs •Information on drug withdrawal may be lacking or unclear

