8.6 Primary Safety analysis

A. Number of participants experiencing Serious Adverse Events (SAEs). [Time Frame: visit 1 to End of study visit].

- Frequency distribution (number & percent) of occurrence of SAEs necessitating a change or discontinuation of treatment. Chi² test will be used to determine p-value and significance between the 2 groups.

- Frequency distribution (number & percent) of type and severity of SAEs. Chi² test will be used to determine *p*-value and significance between the 2 groups.

B. Number of participants experiencing Adverse Events (AEs) leading to permanent discontinuation of the study drug. [Time Frame: visit 1 to End of study visit].

- Frequency distribution (number & percent) of causes of treatment discontinuations. Chi² test will be used to determine *p*-value and significance between the 2 groups.
- Frequency distribution (number & percent) of occurrence of AEs necessitating a change or discontinuation of treatment. Chi² test will be used to determine *p*-value and significance between the 2 groups.
- Frequency distribution (number & percent) of type and severity of AEs. Chi² test will be used to determine *p*-value and significance between the 2 groups.

8.7 Primary Efficacy analysis:

A. Complete resolution for Pelvi- abdominal infection based on pelvi-abdominal Ultrasound

- Frequency distribution (number & percent) of complete resolution for pelvi-abdominal infection. Chi² test will be used to determine *p*-value and significance between the 2 groups.

B. Complete healing of the post-operative wounds [Time Frame: Follow-up 1 V to End of study visit].

- Frequency distribution (number & percent) of complete healing of the post-operative wounds. Chi² test will be used to determine *p*-value and significance between the 2 groups.
- Frequency distribution (number & percent) of incomplete healing of the post-operative wounds. Chi² test will be used to determine *p*-value and significance between the 2 groups.
- Frequency distribution (number & percent) of no healing of the post-operative wounds. Chi² test will be used to determine *p*-value and significance between the 2 groups.

8.8 Secondary Safety analysis:

A. Presence of any signs/symptoms of post-operative wound infection such as redness, fever or wound discharge [Time Frame: visit 1 to End of study visit].

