9.5 Secondary End Point

9.5.1 Secondary Safety:

Table 11 *Number and percent of signs/symptoms of post-operative wound infection among treatment groups*

	Group A (N=156)	Group B (N=156)	p-value
No of signs/symptoms of post-operative wound infection, N (%)			
Redness, N (%)			
Fever, N (%)			
Wound discharge, N (%)			

Table 12 *Percent Change in mean Total leukocytes among treatment groups*

	Group A (N=156)	Group B (N=156)	p-value
Visit 1, mean ± SD			
End of study visit, mean ± SD			
% Change			
p-value between V1 & End of study visit			
p-value between 2 groups			

Table 13 *Percent Change in mean SGOT among treatment groups*

	Group A (N=156)	Group B (N=156)	p-value
Visit 1, mean ± SD			
End of study visit, mean ± SD			
% Change			
p-value between V1 & End of study visit			
p-value between 2 groups			

Table 14 *Percent Change in mean SGPT among treatment groups*

	Group A (N=156)	Group B (N=156)	p-value
Visit 1, mean ± SD			
End of study visit, mean ± SD			
% Change			
p-value between V1 & End of study visit			
p-value between 2 groups			

9.5.2 Secondary Efficacy:

Table 15 Number and percent of complete resolution, improvement, failure or relapse for Pelvi- abdominal infection among treatment groups

	Group A (N=156)	Group B (N=156)	p-value
Complete resolution, N (%)			
Improvement, N (%)			
Failure or relapse, N (%)			

Table 16 *Percent Change in mean days for complete healing of post-operative wounds after 8 days of treatment (Follow up 1 visit) among treatment groups*

	Group A (N=156)	Group B (N=156)	p-value
Visit 1, mean ± SD			
Follow up 1 visit, mean ± SD			
% Change			
p-value between V1 & Follow up 1 visit			
p-value between 2 groups			

Table 17 *Percent Change in mean days for complete healing of post-operative wounds after 15 days of treatment (Follow up 2 visit or End of study visit) among treatment groups*

	Group A (N=156)	Group B (N=156)	p-value
Visit 1, mean ± SD			
Follow up 2 visit, mean ± SD			
% Change			
p-value between V1 & Follow up 2 visit			
p-value between 2 groups			

10 Reference:

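### Wound-infection signs are counted from Visit 1, before any study drug is given, so signs present only at baseline enter a secondary safety comparison and pull it toward no difference

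*Protocol*

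**What the plan says.** Protocol 10.7.8 A gives the outcome and its window as "Presence of any signs/symptoms of post-operative wound infection such as redness, fever or wound discharge [Time Frame: visit 1 to End of study visit". The planned output is "Frequency distribution (number & percent) of presence of any signs/symptoms of post-operative wound infection such as redness, fever or wound discharge", with a Chi² test between groups. SAP 8.8 A repeats the outcome, the window ("Time Frame: visit 1 to End of study visit") and the test, and adds no baseline rule.

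The synopsis defines "Visit 1: Screening and treatment initiation visit, Day 0". Under Visit 1, Protocol 12.3.1 lists among the screening steps: "Presence of any signs/symptoms of post-operative wound infection such as redness, fever or wound discharge will be recorded (in case of post-operative subjects". The same section requires the screening data to be reviewed "by the Investigator to ensure that the subject will be eligible for the study, before dispensing the study drug", and places randomization and first supply after that review. The Visit 1 record therefore precedes both allocation and exposure. The schedule of visits repeats the item at Follow-up 1 and End of study.

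SAP Table 11 has a total row, "No of signs/symptoms of post-operative wound infection, N" (%), and one row each for redness, fever and wound discharge. Each has a single entry per arm under a heading of N=156. There is no row for Visit 1 or for any other visit.

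**The concern.** A sign present before the first tablet is a baseline characteristic. If it is pooled with signs seen on treatment, a patient who had fever at Visit 1 and was well at both follow-up visits counts the same as a patient who developed a wound infection on study drug.

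Two things would follow. The reported percentages would overstate wound infection during treatment in both arms. The between-arm difference would shrink, because the same baseline share is added to each arm. In a safety comparison, a shrunken difference makes it easier to conclude that the regimens are alike.

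The plan treats its neighbouring outcomes differently. Wound healing (10.7.7 B) is counted from Follow-up 1. Leukocytes and liver enzymes (10.7.8 B to D) are analysed as change from Visit 1. The adverse event definition in 13.1 says "This includes events not seen at baseline or worsened if present at baseline". Only the wound-sign outcome puts baseline and on-treatment findings into one count.

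**Working it through.** **The plan's own figure.** Neither document gives a rate, power or sample size for this outcome. The only computed figure, 312, rests on clinical resolution rates. It reproduces with 63% control, 74% experimental, a 2% margin, one-sided 5% and 80% power: (0.63×0.37 + 0.74×0.26) × (1.645 + 0.842)² / (0.02 + 0.11)² ≈ 155.7, so 156 per arm. It does not depend on wound signs and is unaffected by this point.

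**Is anything removed at baseline?** The exclusion criteria (10.2.2) do not exclude patients with wound signs. Neither 10.7.8 A nor SAP 8.8 A limits the count to new signs or adjusts for Visit 1. Table 11 has nowhere to show Visit 1 separately.

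**Could signs be present at Visit 1?** Post-operative patients start oral drug after 48 hours of IV antibiotics or once they tolerate oral intake (10.1). The Introduction (section 6) puts the peak of post-operative complications at one to three days and lists fever among the most common. Baseline signs are therefore plausible, but no prevalence is given.

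**Illustration.** All of the following are assumptions: new-onset rates q of 5% and 15%; Visit 1 prevalence b of 10% or 20%, equal in both arms; and either 78 post-operative patients per arm (half of 156) or all 156.

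- Counted from Visit 1: observed rate = b + (1 − b)q. The difference between arms is multiplied by (1 − b).
- New onset only: rate q among n(1 − b) patients free of signs at Visit 1.
- Power = Φ[(d − 1.96·SE0)/SE1], with SE0 = √(2p̄(1 − p̄)/n) and SE1 = √([p1(1 − p1) + p2(1 − p2)]/n), two-sided 5%.

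Worked case, 156 per arm and b = 20%:

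- From Visit 1: 0.20 + 0.80×0.05 = 24% and 0.20 + 0.80×0.15 = 32%. d = 0.08, SE0 = 0.0508, SE1 = 0.0506. Φ(−0.39) = 35%.
- New onset: n = 124.8, d = 0.10, SE0 = 0.0380, SE1 = 0.0374. Φ(0.68) = 75%.

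| Per arm | b | Rates counted from Visit 1 | Relative risk | Power, from Visit 1 | Sign-free per arm | Power, new onset |
|---|---|---|---|---|---|---|
| 78 | 10% | 14.5% v 23.5% | 1.62 | 30% | 70.2 | 51% |
| 78 | 20% | 24% v 32% | 1.33 | 20% | 62.4 | 46% |
| 156 | 10% | 14.5% v 23.5% | 1.62 | 53% | 140.4 | 80% |
| 156 | 20% | 24% v 32% | 1.33 | 35% | 124.8 | 75% |

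The relative risk for new onset is 3.0 throughout. The power lost by counting Visit 1 signs is 21 and 26 points at 78 per arm, and 27 and 40 points at 156.

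**Other assumed rates.** With new onset of 10% v 20% at 156 per arm, power is 47% against 65% (b = 10%) and 33% against 60% (b = 20%). At 78 per arm and b = 20% it is 19% against 34%.

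**The case against.** **The counting rule is inferred.** Neither document says outright that signs are pooled into one ever-present count. The same bracket is attached to SAEs and AEs in 10.7.6, although the schedule of visits marks no AE collection at Visit 1, so it may be only a generic label for the observation period. Signs are recorded visit by visit, and a by-visit table would fit the text. This stands as a limit on certainty. It does not remove the point: the window names Visit 1, Table 11 has one count per arm, and no by-visit analysis is planned.

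**There is no conflict with the AE definition.** A reader might infer that counting Visit 1 signs contradicts 13.1. It does not. That rule governs adverse events, and wound signs are a separately named endpoint. The difference is an inconsistency of approach.

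**Part of any power loss is unavoidable.** A reader might compare the Visit 1 count with a trial in which nobody has baseline signs, where power would be 55% at 78 per arm and 84% at 156. That overstates the loss. Patients with a sign at Visit 1 cannot have a new onset of it, so a new-onset count also loses patients. The fair comparators are those in the table.

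**Persistence matters for an antibiotic.** Discharge present at Visit 1 and still present at Day 15 is informative, and a count of new signs alone would drop it. This stands and shapes the fix.

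**The outcome is secondary.** Protocol 10.7.5 lists it as something to describe, and it has no sample-size basis. That limits its weight, although a between-group test is planned.

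**Conclusion.** The point holds. Followed as written, both documents put pre-treatment wound signs into a between-arm safety comparison, and no text takes them out. Reading the outcome as one pooled count is the natural reading of the window and Table 11, but it is not stated in words.

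The effect is higher reported rates in both arms and a difference shrunk by the factor (1 − b). A reader might infer that this favours Ciprodiazole. The documents do not support that: Visit 1 signs are recorded before randomization, so baseline prevalence is expected to be equal in the two arms and the distortion is toward no difference.

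Under the assumed 5% v 15% the power cost is 21 to 40 points. It vanishes if no patient has signs at Visit 1. The onset rates, the prevalences and the 78 per arm are all assumptions. The outcome is secondary, so the change is worth making but does not touch the primary analyses.

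**What to change.** - In Protocol 10.7.8 A and SAP 8.8 A, set the time frame to Follow-up 1 to End of study visit.
- In SAP Table 11, replace N=156 with the number of post-operative patients, since the signs are recorded only for them.
- Show presence at Visit 1 as a baseline row, and presence at Follow-up 1 and at End of study as visit rows, each with the number assessed.
- Base the Chi² comparison on new-onset signs among patients free of that sign at Visit 1 (for the total row, free of all signs).
- Show persistent signs, present at Visit 1 and still present at follow-up, in separate rows.
- Do not define the outcome as new or worse. The visits record only presence, so worsening could not be derived without adding a grade to the CRF.

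The cost is wording in two sections and a few more table rows. The signs are already collected at all three visits. The new-onset comparison has a slightly smaller denominator.
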